## 9.4.2. Exposure and Safety Analyses

### 9.4.2.1. Study Drug Administration and Study Drug Compliance

Descriptive information will be provided by treatment arm regarding the number of doses of idelalisib and ofatumumab prescribed, the total number of doses taken, the percent of expected doses taken, the number of days (or infusions) of treatment, and the number and timing of prescribed dose reductions and interruptions.

Idelalisib compliance will be described by treatment arm in terms of the proportion of study drug actually taken based on returned pill count relative to the amount that was dispensed (taking into account physician-prescribed reductions and interruptions).

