## 5.2. Study Drugs

### 5.2.1. Idelalisib

#### 5.2.1.1. Description

For subjects allocated to Arm A of the study, idelalisib will be provided in tablets intended for oral administration. Each tablet contains 150 mg or 100 mg of active idelalisib. The 150-mg tablets will be used for initial therapy; the 100-mg tablets are provided for use by those subjects who require a dose reduction (see [Table 5-2](#)). The 150-mg tablets are pink, film-coated, and include the following inactive excipients: microcrystalline cellulose, hydroxypropyl cellulose, croscarmellose sodium, sodium starch glycolate, magnesium stearate, red iron oxide, polyethylene glycol, talc, polyvinyl alcohol (PVA), and titanium dioxide. The 100-mg tablets are orange, film-coated, and include the following inactive excipients: microcrystalline cellulose, hydroxypropyl cellulose, croscarmellose sodium, sodium starch glycolate, magnesium stearate, yellow iron oxide, polyethylene glycol, talc, PVA, and titanium dioxide.

Details regarding the shape and size of each tablet dosage form will be provided in the pharmacy manual for the study.

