#### 5.2.1.3. Packaging and Labeling

Idelalisib will be provided in bottles. Each bottle contains 60 tablets (4-week supply plus a modest overage) of one of the relevant dose strengths (150 mg or 100 mg) and a polyester coil. Bottles are white and are made of high-density polyethylene. Each bottle is closed with a white, continuous-thread, child-resistant, polypropylene screw cap fitted with an induction-sealed, aluminum-faced liner.

Each bottle will have a label with a unique number. All labels for study drugs to be distributed to centers in the United States and other countries will meet all applicable requirements of the United States Food and Drug Administration (FDA), Annex 13 of Current Good Manufacturing Practice (cGMP) (Manufacture of Investigational Medicinal Products, July 2003), and/or other local regulations as applicable.

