#### Post-Treatment Procedures and Assessments

Idelalisib pharmacokinetics (Arm A)	Post-dose collection of plasma sample for idelalisib pharmacokinetics at 1.5 hours after study drug administration (with recording of the date and actual clock time of blood collection)
Study drug dispensing (Arm A)	Dispensing of 12-week supply of idelalisib to the subject with instructions for self-administration at home

**Abbreviations:**  $\beta$ -HCG=beta human chorionic gonadotropin, AKT=AKT (a serine/threonine protein kinase), ALP=alkaline phosphatase, ALT=alanine aminotransferase, AST=aspartate aminotransferase, DNA=deoxyribonucleic acid, EQ-5D=EuroQoL Five-Dimension, FACT-Leu=Functional Assessment of Cancer Therapy-Leukemia, GGT=gamma-glutamyltransferase, HRQL=health-related quality of life, Ig=immunoglobulin, IWRS=interactive web response system, LDH=lactate dehydrogenase, mTOR=mammalian target of rapamycin, PI3K=phosphatidylinositol 3-kinase, RNA=ribonucleic acid

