**Table 6-8. Procedures and Assessments at Visit 10**

Assessment or Procedure	Explanation
Pre-Treatment Procedures and Assessments	
FACT-Leu	HRQL instrument ( Appendix 2 ) to be administered before any other procedures are performed and before any study-related information is communicated to the subject
EQ-5D	Health utility instrument ( Appendix 4 ) to be administered after FACT-Leu but before other procedures are performed and before study-related information is communicated to the subject
Adverse events	Recording of adverse events occurring since the last clinic visit
Assessment of Diarrhea / Colitis	Obtain history of onset and duration of diarrhea, including description of number of stools and stool composition (eg, watery, bloody, nocturnal), travel history, dietary changes and a medication review to identify possible diarrheogenic agents Perform physical examination including assessment for fever, dizziness, abdominal pain/cramping, and weakness (ie, evaluate for sepsis, bowel obstruction, dehydration)
Concomitant medications	Recording of concomitant medication use since the last clinic visit
Study drug return/accounting	Counting returned idelalisib
Performance status	Using Karnofsky performance status criteria ( Appendix 3 )
Oxygen saturation	To be assessed by pulse oximetry while subject is breathing room air
Physical examination	Including assessment of weight, lymph nodes, spleen, and liver
Urine $\beta$ -HCG dipstick	For women of child-bearing potential only
Hematology	Including hematocrit, hemoglobin, erythrocyte count; absolute counts of leukocytes, neutrophils, lymphocytes, monocytes, eosinophils, basophils, platelet count
Serum chemistry	Including sodium, potassium, chloride, glucose, urea, creatinine, calcium, phosphorus, total protein, albumin, ALT, AST, ALP, GGT, total bilirubin, LDH, uric acid, cholesterol, triglycerides
HBV DNA by PCR	Only subjects who are HBc antibody positive and HBV DNA negative at screening, per Section 5.4.5 .
Circulating cells	Including cells for analysis of PI3K/AKT/mTOR pathway activation and quantitation of CD4+, CD5+, CD8+, CD16/CD56+, CD19+, and CD+20 cells by flow cytometry
Biomarkers	Collection of plasma and serum for evaluation of circulating chemokines and cytokines
Serum Igs	Including quantitative levels of IgA, IgE, IgG, and IgM

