#### 9.3.1.2. Per-Protocol Analysis Set

The PP analysis set includes data from subjects in the ITT analysis set who meet the general criteria defining the target population for this study, are adherent to the protocol, are compliant with study drug treatment, and are evaluable for relevant efficacy endpoints. Study drug assignment will be designated according to the actual treatment received. The specific classification of subjects to be included in the PP analysis set will be included in the statistical analysis plan which will be finalized prior to database lock.

The PP analysis set will be used in sensitivity analyses of the primary and the following secondary efficacy variables: PFS, ORR, lymphadenopathy node response rate, and PFS in the subgroup of subjects with 17p deletion and/or TP53 mutation.

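### Idelalisib compliance is measured against tablets dispensed, so a fully adherent subject scores about 86% in the 77-day first interval and 93% in later intervals

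*Protocol*

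**What the plan says.** Section 9.4.2.1 defines compliance as "the proportion of study drug actually taken based on returned pill count relative to the amount that was dispensed". The one adjustment it names is "taking into account physician-prescribed reductions and interruptions". Earlier in the section, as a separate exposure summary, it also lists "the percent of expected doses taken".

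The supply rules are elsewhere in the protocol:

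- Section 5.2.1.3: "Each bottle contains 60 tablets (4-week supply plus a modest overage".
- Section 5.2.1.1: "Each tablet contains 150 mg or 100 mg of active idelalisib". Table 5-2 gives the dose levels as 150 mg BID and 100 mg BID, so either level is one tablet twice a day.
- Section 5.2.1.5: drug is issued every 12 weeks in unopened original bottles. The table for Visit 2 has "Dispensing of 12-week supply of idelalisib to the subject", and Visits 10, 13, 15, 17 and later dispensing visits repeat it.
- Section 5.2.1.6: unused tablets are collected when each interval closes. Table 6-8 (Visit 10) has the first count: "Counting returned idelalisib".
- Table 5-1 and Appendix 7: dispensing visits fall on Days 1, 78, 162, 246 and 330.

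Section 9.3.1.2 requires per-protocol subjects to be those who, among other things, "are compliant with study drug treatment". It leaves the exact classification to the SAP.

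**The concern.** A compliance ratio should read 100% for a subject who takes every prescribed dose. This denominator counts tablets that the subject was never meant to take: the overage in each bottle, and the surplus left when a 12-week supply is issued for a shorter interval. Neither is a prescribed reduction or interruption, so the stated adjustment does not remove them.

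Two things are at stake. The reported figure would make adherence to idelalisib look worse than it was. It would also differ between subjects with identical adherence, because the size of the artefact depends on how long they stayed on treatment and when their visits fell.

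**Working it through.** **Supply check (the protocol's own figure).** Four weeks at two tablets a day need 28 × 2 = 56 tablets. A bottle holds 60, leaving 60 − 56 = 4 spare, which agrees with Section 5.2.1.3.

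**Tablets dispensed per 12-week supply.** Twelve weeks need 84 × 2 = 168 tablets. Two bottles (120) are too few, so three are needed: 3 × 60 = 180, of which 3 × 4 = 12 are overage. Three bottles is an inference, but it follows from the bottle size and the instruction to use original bottles.

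**Score of a fully adherent subject.** Score = 2 × days in interval ÷ 180, at nominal visit days.

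| Interval | Days | Tablets taken | Unused | Score |
|---|---|---|---|---|
| Day 1 to 78 | 77 | 154 | 26 | 154/180 = 85.6% |
| Day 78 to 162 | 84 | 168 | 12 | 168/180 = 93.3% |
| Day 162 to 246 | 84 | 168 | 12 | 93.3% |
| Day 246 to 330 | 84 | 168 | 12 | 93.3% |

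**Source of the shortfall.** In later intervals all 12 unused tablets are overage. In the first interval 12 are overage and (84 − 77) × 2 = 14 come from the short interval. The short interval is thus the larger cause of the 85.6%.

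**Cumulative score at full adherence.**

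- By Day 162: (154 + 168)/360 = 322/360 = 89.4%.
- By Day 330: (154 + 3 × 168)/720 = 658/720 = 91.4%.

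**Sensitivity.**

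- Counting one in-clinic dose differently gives 85.0% to 86.1% in the first interval and 92.8% to 93.9% later.
- Moving the closing visit by its 3-day window gives 82.2% to 88.9% and 90.0% to 96.7%.
- If both ends of a later interval shift to give 90 days, the score is 180/180 = 100%.

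**Shape of the bias.** The ratio multiplies true intake by 0.856 or 0.933. A subject who took half the doses reads 0.5 × 154/180 = 42.8% or 0.5 × 168/180 = 46.7%, an understatement of about 7 or 3 points.

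**With prescribed tablets as denominator.** Full adherence gives 154/154 and 168/168, both 100%.

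**The case against.** The strongest reply is that this is one descriptive sentence whose algorithm belongs in the SAP. On that view the reference to dispensed tablets only explains how tablets taken are counted, and the adjustment for prescribed changes implies a comparison with what should have been taken. That reading is possible but not the plain one, because the sentence names a numerator and a denominator. If it is what was meant, the sentence still needs rewording.

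A second reply stands in part. The section already plans the percentage of expected doses taken, so a reader of the study report would have a sound figure alongside. That limits the harm but does not correct the quantity labelled compliance.

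A reader might go further and infer that adherent Arm A subjects would be dropped from the per-protocol set. Under an assumed 80% cut-off, a subject taking 93% of first-interval doses reads 0.93 × 154/180 = 79.6%. The protocol does not support that inference. Section 9.3.1.2 neither refers to this ratio nor sets a cut-off, and nothing says compliance is judged interval by interval. Cumulatively the same subject reads 0.93 × 322/360 = 83.2% by Day 162 and 0.93 × 658/720 = 85.0% by Day 330.

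**Conclusion.** The point holds as a minor defect in a stated rule. At nominal visit days, with three bottles per 12-week supply, full adherence reads 85.6% in the first interval and 93.3% in later ones.

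Three stronger statements should be avoided:

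- Overage alone does not produce the 86%; it accounts for 12 of the 26 unused tablets.
- Compliance is not understated by 7 to 14 points for every subject, because the bias is proportional to intake.
- The ratio can reach 100%, for example when visit windows stretch a later interval to 90 days.

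The consequence is limited to the descriptive compliance summary, which concerns Arm A only because idelalisib is given only there. The per-protocol sensitivity analyses would be affected only if the SAP adopts this ratio for membership. The primary PFS analysis is in the ITT set and does not use it.

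**What to change.** In Section 9.4.2.1, define idelalisib compliance as tablets taken (dispensed minus returned) divided by tablets prescribed between the dispensing and return dates, after prescribed reductions and interruptions. If the SAP sets a compliance threshold for the per-protocol set, base it on this figure.

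The change is one line of text. The dispensing and return records and the prescribed dosing it needs are already collected.

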### 9.4.2.2. Idelalisib Plasma Concentrations

The idelalisib plasma concentrations immediately pre-dose and at 1.5 hours after administration of the dose of study drug at each relevant clinic visit among subjects treated on Arm A of the study will be summarized and visit using descriptive statistics.

### 9.4.2.3. Prior and Concomitant Medication Use

Prior and concomitant medications will be coded by means of the World Health Organization Drug Dictionary (WHODRUG) dictionary into Anatomical-Therapeutic-Chemical classification (ATC) codes.

Descriptions of prior medication use will be focused on drugs and regimens used as treatments for CLL. To the extent available, information on the sequencing, type, dose, schedule, timing, duration of use, and efficacy of prior regimens will be provided.

The type and timing of use of concomitant medications will be listed and summarized by type and treatment arm. Information regarding the type and use of specific supportive medications (eg, pneumocystis prophylaxis, hematopoietic growth factors, and corticosteroids) during study treatment, and within 30 days post-study treatment, will be described.

### 9.4.2.4. Adverse Events

All adverse events will be listed. The focus of adverse event summarization will be on treatment-emergent adverse events. A treatment-emergent adverse event is defined as an adverse event that occurs or worsens in the period from the first dose of study treatment (idelalisib or ofatumumab) to 30 days after the last dose of study drug.

Adverse events will be classified using MedDRA (<http://www.meddra.org>) with descriptions by System Organ Class, High-Level Group Term, High-Level Term, Preferred Term, and Lower-Level Term. The severity of adverse events will be graded by the investigator according to the CTCAE, Version 4.03 ([http://evs.nci.nih.gov/ftp1/CTCAE/CTCAE\\_4.03\\_2010-06-14\\_QuickReference\\_8.5x11.pdf](http://evs.nci.nih.gov/ftp1/CTCAE/CTCAE_4.03_2010-06-14_QuickReference_8.5x11.pdf)), whenever possible. If a CTCAE criterion does not exist for a specific type of adverse event, the grade corresponding to the appropriate adjective will be used

by the investigator to describe the maximum intensity of the adverse event: Grade 1 (mild), Grade 2 (moderate), Grade 3 (severe), Grade 4 (life threatening), or Grade 5 (fatal). The relationship of the adverse event to the study drug will be categorized as related or unrelated.

Separate listings and summaries will be prepared for the following types of treatment-emergent adverse events:

- Study-treatment-related (idelalisib or ofatumumab) adverse events
- Adverse events that are Grade  $\geq 3$  in severity
- Adverse events leading to study treatment (idelalisib or ofatumumab) interruption and/or dose modification
- Adverse events leading to study drug (idelalisib or ofatumumab) discontinuation
- Serious adverse events (with categorization of the primary reason that the adverse event is considered serious, eg, death, hospitalization, etc)

The severity of ofatumumab-related infusion reactions and of the total durations of ofatumumab infusions will be compared between treatment arms to determine whether idelalisib pretreatment modifies the magnitude of such events or alters the length of the ofatumumab infusion due to such events; the focus of this analysis will be on the first 2 ofatumumab infusions (ie, those on Study Day 1 and on Day 8). However, assessment of infusion reaction severity and duration will be performed for all 12 planned infusions of ofatumumab. Comparisons will be done using the Chi-square test for severity grade and the Wilcoxon rank-sum test for infusion duration.

Separate listings and summaries will be prepared for long-term follow-up safety data.

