### Randomization and Stratification

- 2:1 allocation to Arm A vs Arm B with implementation through an interactive web response system (IWRS)
- Fixed-block centralized randomization with allocation of subjects within the 8 strata as defined by the intersection of 3 binary stratification factors:
- 17p deletion and/or TP53 mutation in CLL cells: either vs neither (or indeterminate)
- Immunoglobulin heavy chain variable region (IgHV) mutation: unmutated (or IgHV3-21) vs mutated (or indeterminate)
- Disease status: refractory (CLL progression < 6 months from completion of prior therapy) vs relapsed (CLL progression ≥6 months from completion of prior therapy)

Number of  
Subjects  
Planned:

Total of ~255 subjects (~170 subjects in Arm A and ~85 subjects in Arm B)

Target Population:	
The target population comprises adults with previously treated CLL who have measurable lymphadenopathy, require treatment for CLL, have disease that is not refractory to ofatumumab, and might benefit from a change in therapy because they have experienced CLL progression < 24 months since the completion of the last prior treatment.

Duration of Treatment:	
Idelalisib will be taken continuously until the earliest of subject withdrawal from study, definitive progression of CLL, intolerable study drug-related toxicity, pregnancy, substantial noncompliance with study procedures, or study discontinuation. Idelalisib administration should be continued in subjects with a positive benefit-risk profile assessment as per the investigator.
 
Ofatumumab will be administered until the earliest of a maximum of 12 infusions, subject withdrawal from study, definitive progression of CLL, intolerable ofatumumab-related toxicity, pregnancy, substantial noncompliance with study procedures, or study discontinuation.
 
Subjects in Arm A will continue with idelalisib or ofatumumab, even if the other drug must be discontinued due to toxicity.

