- Arm A: Ofatumumab: 300 mg intravenously on Day 1 (Week 1); thereafter 1,000 mg intravenously on Day 8 (Week 2), Day 15 (Week 3), Day 22 (Week 4), Day 29 (Week 5), Day 36 (Week 6), Day 43 (Week 7), Day 50 (Week 8), Day 78 (Week 12), Day 106 (Week 16), Day 134 (Week 20), Day 162 (Week 24) (for a total of 12 infusions)

- Arm B: Ofatumumab: 300 mg intravenously on Day 1 (Week 1); thereafter 2,000 mg intravenously on Day 8 (Week 2), Day 15 (Week 3), Day 22 (Week 4), Day 29 (Week 5), Day 36 (Week 6), Day 43 (Week 7), Day 50 (Week 8), Day 78 (Week 12), Day 106 (Week 16), Day 134 (Week 20), Day 162 (Week 24) (for a total of 12 infusions)

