#### 5.4.3.1. Investigation for Idelalisib Late Onset or Severe Diarrhea/Colitis

See CTCAE Version 4.03 for definitions of colitis and diarrhea.

Among idelalisib-treated patients who reported diarrhea or colitis, the median time to onset of any grade diarrhea or colitis was 1.9 months (range, 0.0–29.8), of grade 1 or 2 was 1.5 months (range, 0.0–15.2) and of grade 3 or 4 was 7.1 months (range, 0.5–29.8). Kaplan–Meier curves of time to onset of diarrhea or colitis are shown for all idelalisib- treated patients in [Figure 5-1](#)

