**Table 6-12. Procedures and Assessments at Visits 14 and 16**

Assessment or Procedure	Explanation
FACT-Leu	HRQL instrument ( Appendix 2 ) to be administered before any other procedures are performed and before any study-related information is communicated to the subject
EQ-5D	Health utility instrument ( Appendix 4 ) to be administered after FACT-Leu but before other procedures are performed and before study-related information is communicated to the subject
Adverse events	Recording of adverse events occurring since the last clinic visit
Assessment of Diarrhea / Colitis	Obtain history of onset and duration of diarrhea, including description of number of stools and stool composition (eg, watery, bloody, nocturnal), travel history, dietary changes and a medication review to identify possible diarrheogenic agents Perform physical examination including assessment for fever, dizziness, abdominal pain/cramping, and weakness (ie, evaluate for sepsis, bowel obstruction, dehydration)
Concomitant medications	Recording of concomitant medication use since the last clinic visit
Performance status	Using Karnofsky performance status criteria ( Appendix 3 )
Oxygen saturation	To be assessed by pulse oximetry while subject is breathing room air
Physical examination	Including assessment of weight, lymph nodes, spleen, and liver
Urine $\beta$ -HCG dipstick	For women of child-bearing potential only
Hematology	Including hematocrit, hemoglobin, erythrocyte count; absolute counts of leukocytes, neutrophils, lymphocytes, monocytes, eosinophils, basophils, platelet count
Serum chemistry	Including sodium, potassium, chloride, glucose, urea, creatinine, calcium, phosphorus, total protein, albumin, ALT, AST, ALP, GGT, total bilirubin, LDH, uric acid, cholesterol, triglycerides
Circulating cells	Including cells for analysis of PI3K/AKT/mTOR pathway activation and quantitation of CD4+, CD5+, CD8+, CD16/CD56+, CD19+, and CD+20 cells by flow cytometry
Biomarkers	Collection of plasma and serum for evaluation of circulating chemokines and cytokines
CMV Surveillance	Arm A only: Surveillance for active disease must be conducted approximately every 4 weeks.
Serum Igs	Including quantitative levels of IgA, IgE, IgG, and IgM
IWRS access	Access of IWRS to document subject visit and to obtain kit numbers (if applicable)

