### **8.3. Investigator Requirements and Instructions for Reporting Adverse Events and Serious Adverse Events to Gilead or Designee**

All SAEs, regardless of cause or relationship, that occur after the subject first consents to participate in the study (ie, signing the informed consent) and throughout the duration of the study, including the protocol-required post treatment follow-up period, must be reported to the eCRF database and Gilead Drug Safety and Public Health (DSPH) or designee as instructed. This also includes any SAEs resulting from protocol-associated procedures performed from screening onwards.

All AEs, regardless of cause or relationship, that occur from initiation of study medication until 30 days after last administration of study IMP must be reported to the eCRF database as instructed.

Any SAEs and deaths that occur after the post treatment follow-up visit but within 30 days of the last dose of study IMP, regardless of causality, should also be reported.

All AEs should be followed up until resolution if possible. If by the last day on study (including the off-study medication follow-up period) the AE has not resolved, then the AE will be followed up until the investigator and/or Gilead Sciences determine that the subject's condition is stable. However, Gilead Sciences may request that certain AEs be followed until resolution.

Investigators are not obligated to actively seek SAEs after the 30 day period. However, if the investigator learns of any SAEs that occur after study participation has concluded and the event is deemed relevant to the use of IMP, he/she should promptly document and report the event to Gilead DSPH or designee as instructed.

All AEs and SAEs will be recorded in the eCRF database within the timelines outlined in the eCRF completion guidelines.

SAEs will be reported using a paper SAE reporting form. During the course of the study, there may be a transition to an electronic SAE (eSAE) system. Gilead will notify sites in writing and provide training and account information prior to implementing an eSAE system.

All SAEs will be recorded on the SAE report form and submitted by faxing the report form within 24 hours of the investigator's knowledge of the event to the attention of Gilead DSPH or to the designated CRO.

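### Non-serious AE reporting and the AE summaries stop 30 days after last dose, near Day 192 in Arm B but open-ended in Arm A, and the visit tables say otherwise

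*Protocol*

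**What the plan says.** Section 9.4.2.4 makes treatment-emergent events the focus of the adverse event (AE) summaries and defines them as events that occur or worsen "from the first dose of study treatment (idelalisib or ofatumumab) to 30 days after the last dose of study drug". The separate summaries it lists (treatment-related, Grade 3 or higher, leading to interruption or discontinuation, and serious) are all subsets of those events.

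Section 8.3 sets the reporting duty. AEs in general are those "that occur from initiation of study medication until 30 days after last administration of study IMP must be reported to the eCRF database as instructed". Serious AEs (SAEs) have a longer rule and are reported "throughout the duration of the study, including the protocol-required post treatment follow-up period".

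Treatment duration differs by design. The synopsis says that "Ofatumumab will be administered until the earliest of a maximum of 12 infusions" or an earlier stop, and its schedule ends with "Day 106 (Week 16), Day 134 (Week 20), Day 162 (Week 24) (for a total of 12 infusions". Ofatumumab is the only study drug in Arm B. Idelalisib in Arm A is continuous until progression, intolerable toxicity or another listed reason.

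Under Section 5.9, subjects who stop drug without progression stay on the assessment schedule. Table 6-12 (Visits 14 and 16, Days 204 and 288) calls for "Recording of adverse events occurring since the last clinic visit", with no restriction by arm. Tables 6-13 and 6-14 and Appendix 7 do the same for Visits 15, 17 and 18 onward.

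**The concern.** The same rule, last dose plus 30 days, produces very different observation periods when one arm has a fixed 24-week course and the other an open-ended one. An event with the same hazard in both arms will then show a higher percentage in Arm A simply because Arm A is watched for longer. Section 3.2 makes the safety profile of adding idelalisib a stated objective, so this comparison matters.

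There is also a data-capture problem. After about Day 192 a site with an Arm B subject still on study has two instructions. The visit tables tell it to record AEs, while Section 8.3 no longer requires non-serious ones to be reported. Sites that follow Section 8.3 literally will not enter them, and no later analysis can recover them. Late SAEs in Arm B will be reported, but the SAE summary in Section 9.4.2.4 leaves them out because they are not treatment-emergent.

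**Working it through.** **Arm B closing date.** Eight weekly infusions starting on Day 1 put the eighth on Day 1 + 7 × 7 = 50. Four more at 28-day intervals give 50 + 4 × 28 = Day 162, as the synopsis states. Adding 30 days gives Day 192. One maximal 4-week delay (Section 5.4.4) gives 162 + 28 + 30 = Day 220. Early stopping of ofatumumab closes the window sooner.

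**Who is still on study.** Section 9.5 assumes exponential PFS with medians of 8 months (Arm B) and 14 months (Arm A). Taking 30.44 days per month, 192 days is 6.31 months, and the Arm B proportion progression-free is 2^(−6.31/8) = 0.58. So about 58% of Arm B would still be attending visits after its window has closed. In Arm A, 2^(−5.32/14) = 0.77 are progression-free at Day 162, and the window stays open for those still on idelalisib.

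**Check on the PFS inputs.** The protocol gives no figure for window length to reproduce. Its event count can be checked: the Schoenfeld formula with HR 0.57, 2:1 allocation and two-sided 0.05 gives 128 events for 85% power, and 129 events give 85.3%. The stated 129 is consistent.

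**Expected window length.** For Arm B, mean time on drug is (1 − 2^(−5.32/8)) ÷ (ln 2/8) = (1 − 0.631) ÷ 0.0866 = 4.26 months. Adding 30 days (0.99 month) gives 5.25 months. For Arm A the data cut matters. Accrual follows Section 9.5 (12 months, half the subjects in the first 7.2), so mean entry is at month 6.6. Two cuts were used:
- month 19.3, close to the 129-event analysis (133 events expected before any loss to follow-up);
- month 24, the end of the planned minimum follow-up.

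Mean potential follow-up is then 12.7 and 17.4 months. The Arm A windows were simulated. As a check, a fixed 12.7 months of follow-up gives 0.99 + (1 − e^(−0.0495 × 11.7)) ÷ 0.0495 = 9.9 months, against 9.7 simulated with staggered entry.

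**Incidence with no drug effect.** The AE hazard is an assumption: 20% over 192 days, or h = −ln(0.8)/6.31 = 0.0354 per month, constant and equal in both arms. Incidence is the mean of 1 − e^(−h × window). The documents give no rate of stopping idelalisib for reasons other than progression, so 0, 20 and 40% per year were assumed.

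| Cut (month) | Other stopping per year | Mean window A / B (months) | Incidence A / B | Ratio |
|---|---|---|---|---|
| 19.3 | 0% | 9.7 / 5.25 | 28% / 17% | 1.68 |
| 19.3 | 20% | 8.9 / 5.25 | 26% / 17% | 1.55 |
| 19.3 | 40% | 8.0 / 5.25 | 24% / 17% | 1.41 |
| 24 | 0% | 12.1 / 5.25 | 33% / 17% | 1.98 |
| 24 | 20% | 10.7 / 5.25 | 30% / 17% | 1.79 |
| 24 | 40% | 9.3 / 5.25 | 27% / 17% | 1.58 |

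Two sensitivities follow. If the hazard after 192 days falls to a quarter of its early value (assumed), the ratios drop to about 1.1 to 1.3. At month 24, changing the assumed rate to between 0.1 and 0.6 per patient-year gives ratios of about 1.5 to 2.2; the rarer the event, the closer the ratio comes to that of the windows themselves.

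**The case against.** A 30-day post-dose window is a conventional definition, and unequal exposure is inherent in adding a continuous drug to a fixed course. That is fair: the definition is not an error in itself, and the treatment-emergent summary should stay.

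A reader might go further and infer that Arm B becomes unobserved for safety after Day 192. The documents do not support this. Section 8.3 keeps SAE reporting open throughout the study in both arms, the visit tables continue AE recording, and Section 8.3 states what must be reported without forbidding later entries. The gap concerns non-serious AEs, which can include Grade 3 events that meet no seriousness criterion.

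A reader might also infer that late events have no concurrent control, because Section 5.4.3.1 says the median onset of diarrhea or colitis "of grade 3 or 4 was 7.1 months". That is too strong. The figure is a median among idelalisib-treated patients who reported such events, with a range of 0.5 to 29.8 months, so about half came earlier. At 7.1 × 30.44 = Day 216 it falls only narrowly after Day 192, and before Day 220 if one maximal delay has occurred. Late cases that are serious are reportable in Arm B.

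Nor does the protocol put the analysis beyond repair. Section 9.4.2.4 does not exclude exposure-adjusted rates or a common-window table, and a SAP could add either from data collected as Section 8.3 requires. What a SAP cannot supply is non-serious Arm B events after the window that were never entered. All AEs are to be listed, and long-term follow-up safety data are summarized separately, but a listing is not a comparison, and that follow-up is annual from the end-of-study visit.

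**Conclusion.** The point holds in this limited form. Section 8.3 and the visit tables disagree on whether non-serious AEs are captured in Arm B after about Day 192, when some 58% of that arm would still be on study under the protocol's own PFS assumption. The AE summaries, including the SAE summary, are confined to windows averaging about 5 months in Arm B and 8 to 12 months in Arm A. With equal constant hazards (20% per 192 days) this alone gives incidence ratios of about 1.4 to 2.0.

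That size rests on the assumed AE hazard, on 0 to 40% per year of other idelalisib stopping, and on a cut at 19.3 or 24 months; a declining hazard makes it smaller. No single ratio should be quoted as the bias. The direction was the same in every scenario examined. Efficacy analyses are unaffected. This should be corrected, because part of the loss occurs at data capture.

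**What to change.** In Section 8.3, require all AEs to be recorded in both arms until the end of study participation, in line with Tables 6-12 to 6-14 and Appendix 7. Starting other anticancer therapy is already among the reasons in Section 5.9 for ending participation, which limits contamination from later treatment.

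In Section 9.4.2.4, keep the treatment-emergent summary and put two tables beside it: exposure-adjusted incidence rates by arm, and incidence within a common window of Day 1 to 192. Both are still needed after the Section 8.3 change, because participation itself is expected to end earlier in Arm B through earlier progression.

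The cost is some additional AE entry for Arm B at visits already scheduled, a wording change and two tables. No visit is added and treatment is unchanged.
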